3.2. Phase 1b Dose Escalation and Expansion Overview

Phase 1b will be conducted in the United States (US), with approximately 46 subjects enrolled. Additional subjects may be screened and enrolled in any cohort as outlined. In the dose escalation portion, up to four dose levels of lenalidomide will be explored and the dose escalation will follow the 3+3+3 principles. The decision to expand any individual cohort up to

9 subjects for the purpose of safety evaluation will be made after review of the dose escalation safety data.

During Phase 1b the doses of both ibrutinib and rituximab will remain fixed with up to 4 dose levels of lenalidomide to be explored according to cohort ([Table 4](#)). After completion of Cohort 1 at Dose Level 1, due to 3 DLTs in 7 evaluable subjects, a cohort at Dose Level -1 was opened. After completion of the Dose Level -1 cohort, if <33% of subjects experience a DLT, dose re-escalation to higher dose levels starting with the lenalidomide dose of 15 mg may occur. Both ibrutinib and lenalidomide will continue until disease progression or unacceptable toxicity, while rituximab will be discontinued after 6 cycles. See [Section 5](#) for study treatment details.

After completion of Phase 1b Cohort 2 at Dose Level 2 (20 mg lenalidomide), enrollment into Phase 2 will commence with 20 mg lenalidomide, if determined to be safe and tolerated in the Phase 1b portion of the study. Concurrent with the Phase 2 at 20 mg lenalidomide, Phase 1b Cohort 3 at Dose Level 3 (25 mg lenalidomide) may be enrolled.

3.3. Phase 2 Efficacy Evaluation Overview

Phase 2 will be an open-label, international, multi-center study. This portion of the study will be conducted at up to 70 international clinical centers, with approximately 55 subjects enrolled. Subjects will be treated with the 20 mg lenalidomide dose, if determined to be safe and tolerated in the Phase 1b portion of the trial.

An interim analysis will be performed as outlined in [Section 10](#).

4. SUBJECT SELECTION

The inclusion and exclusion criteria for enrolling subjects on this study are described below. If there are any questions about the entry criteria, the Investigator should consult with the Medical Monitor before enrolling a subject in the study. Selected eligibility criteria must be confirmed in writing by the Medical Monitor prior to enrollment.

4.1. Inclusion Criteria

To be enrolled in the study, each potential subject must satisfy all of the following inclusion criteria.

Disease Related

1. Pathologically confirmed:
 - a. Phase 1b: diffuse large B-cell lymphoma.
 - b. Phase 2: de novo non-GCB DLBCL by Hans method testing using immunohistochemistry

Note: Sufficient tissue sample for evaluation by IHC and GEP is required for subjects in Phase 2 (refer to Laboratory Manual for requirements).

2. Relapsed or refractory disease, such as either: 1) recurrence of disease after a complete response (CR), or 2) partial response (PR), stable disease (SD) or progressive disease (PD) at completion of the treatment regimen preceding entry to the study (residual disease).
3. Subjects must have previously received an appropriate first-line treatment regimen.
4. For subjects having a computed tomography (CT) scan abnormality with uncertain interpretation following completion of the most recent treatment regimen: biopsy confirmation of residual DLBCL is required prior to study entry to confirm residual DLBCL and to rule out a non-lymphomatous process (eg, fibrosis).
5. Subjects who have not received HDT/SCT must be ineligible for HDT/SCT as defined by meeting any of the following criteria:
 - a. Age \geq 70 years.
 - b. Diffuse lung capacity for carbon monoxide $<50\%$ by pulmonary function test.
 - c. Left ventricular ejection fraction $<50\%$ by multiple gated acquisition/echocardiogram.
 - d. Other organ dysfunction or co-morbidities precluding the use of HDT/SCT on the basis of unacceptable risk of treatment-related morbidity.
 - e. Failure to achieve PR or CR with salvage therapy.
 - f. Subject refusal of HDT/SCT.
6. One or more measurable disease sites on CT scan (>1.5 cm in longest dimension). Lesions in anatomical locations (such as extremities or soft tissue lesions) that are not well visualized by CT may be measured by MRI instead (see [Section 7.3.1](#)).

Laboratory

7. Adequate hematologic function with screening laboratory assessment independent of growth factor and transfusion support for at least 7 days, with the exception of pegylated G-CSF (pegfilgrastim) and darbepoetin which require at least 14 days, defined as:
 - a. Absolute neutrophil count (ANC) $>1,500$ cells/ mm^3 ($1.5 \times 10^9/\text{L}$).
 - b. Platelet count $>75,000$ cells/ mm^3 ($75 \times 10^9/\text{L}$).
 - c. Hemoglobin >8.0 g/dL.
8. Adequate hepatic and renal function with screening laboratory assessment defined as:
 - a. Serum aspartate transaminase (AST) or alanine transaminase (ALT) $\leq 2.5 \times$ upper limit of normal (ULN).
 - b. Creatinine clearance (Cockcroft-Gault or 24-hour creatinine clearance collection) >60 mL/min.
 - c. Bilirubin $<1.5 \times$ ULN [unless bilirubin rise is due to Gilbert's syndrome (as defined by $>80\%$ unconjugated hyperbilirubinemia) or of non-hepatic origin].
9. PT/INR $<1.5 \times$ ULN and aPTT $<1.5 \times$ ULN.

Demographic

10. Men and women \geq 18 years of age.
11. Eastern Cooperative Oncology Group (ECOG) performance status of <2.

Ethical/Other

12. All study participants must be registered into the mandatory Revlimid REMS™ program, and be willing and able to comply with the requirements of the Revlimid REMS™ program **(for US sites only)**.
13. Female subjects of childbearing potential (FCBP)^a must have a negative serum or urine pregnancy test with a sensitivity of at least 25 mIU/mL within 10 – 14 days and again within 24 hours prior to prescribing lenalidomide for Cycle 1 (prescriptions must be filled within 7 days as required by Revlimid REMS™) and must either commit to continued abstinence from heterosexual intercourse or begin TWO acceptable methods of birth control, one highly effective method and one additional effective method AT THE SAME TIME, at least 28 days before she starts taking lenalidomide. Female subjects of childbearing potential (FCBP) must also agree to ongoing pregnancy testing. See [Appendix 7 \(for US sites only\)](#).
14. Female subjects of childbearing potential (FCBP)^a must have a negative serum or urine pregnancy test with a sensitivity of at least 25 mIU/mL within 10 – 14 days and again within 24 hours prior to starting Cycle 1 of lenalidomide. FCBP must also agree to ongoing pregnancy testing. All subjects must be counseled at a minimum of every 28 days about pregnancy precautions and risks of fetal exposure. See [Appendix 8 \(for ex-US sites only\)](#).
15. Male subjects must agree to use a latex condom during sexual contact with a FCBP even if they have had a successful vasectomy. See **(for US sites only)**.
16. Male subjects must agree to use a latex condom during sexual contact with a FCBP even if they have had a successful vasectomy. All subjects must be counseled at a minimum of every 28 days about pregnancy precautions and risks of fetal exposure. See [Appendix 8 \(for ex-US sites only\)](#).
17. Female subjects of child bearing potential (FCBP)^b and male subjects who are sexually active must use TWO acceptable methods of birth control, one highly effective method of birth control plus one additional effective method of birth control for at least 28 days prior to study treatment and during the study treatment period. For female subjects, these birth control requirements must be adhered to for 12 months after the last dose of rituximab or 30 days after the last dose of ibrutinib and lenalidomide, whichever is later. For male subjects, these birth control requirements must be adhered to for 90 days after the last dose of ibrutinib and lenalidomide, whichever is later. Male subjects must agree to not donate sperm during the study treatment period and up to 90 days after the last dose of ibrutinib and lenalidomide.
18. Life expectancy of more than 3 months.

^b A female of childbearing potential (FCBP) is a sexually mature female who: 1) has not undergone a hysterectomy or bilateral oophorectomy; or 2) has not been naturally postmenopausal for at least 24 consecutive months (ie, has had menses at any time in the preceding 24 consecutive months).

4.2. Exclusion Criteria

To be enrolled in the study, potential subjects must not have any of the following exclusion criteria:

Disease-Related

Phase 2 Only

1. Transformed DLBCL, germinal center B-cell (GCB) DLBCL or DLBCL with coexistent histologies (eg, follicular or mucosa-associated lymphoid tissue [MALT] lymphoma).
2. Primary mediastinal (thymic) large B-cell lymphoma.

Phase 1b/2

3. Medically apparent central nervous system lymphoma or leptomeningeal disease.
4. History of allogeneic stem-cell (or other organ) transplantation.
5. Any chemotherapy, external beam radiation therapy, or anticancer antibodies within 2 weeks of the first dose of study drug.
6. Radio- or toxin-immunoconjugates within 10 weeks of the first dose of study drug.
7. Concurrent enrollment in another therapeutic investigational study or have previously taken ibrutinib and/or lenalidomide.

Concurrent Conditions

8. History of other malignancies, except:
 - a. Malignancy treated with curative intent and with no known active disease present for ≥ 5 years before the first dose of study drug and felt to be at low risk for recurrence by treating physician.
 - b. Adequately treated non-melanoma skin cancer or lentigo maligna without evidence of disease.
 - c. Adequately treated carcinoma in situ without evidence of disease.
9. Concurrent systemic immunosuppressant therapy (eg, cyclosporine A, tacrolimus, etc., or chronic administration of >20 mg/day of prednisone) within 28 days of the first dose of study drug.
10. Recent infection requiring intravenous anti-infective treatment that was completed ≤ 14 days before the first dose of study drug.
11. Unresolved toxicities from prior anticancer therapy, defined as having not resolved to Common Terminology Criteria for Adverse Event ([CTCAE, version 4.03](#)), Grade ≤ 1 or to the levels dictated in the inclusion/exclusion criteria with the exception of alopecia.
12. Known bleeding diathesis (eg, von Willebrand's disease) or hemophilia.
13. Known history of human immunodeficiency virus (HIV) or chronic or active hepatitis C virus (HCV) or hepatitis B virus (HBV) infection.

14. Major surgery within 4 weeks of first dose of study drug.
15. Currently active, clinically significant cardiovascular disease, such as uncontrolled arrhythmia or class 3 or 4 congestive heart failure as defined by the New York Heart Association Functional Classification; or a history of myocardial infarction, unstable angina, or acute coronary syndrome within 6 months prior to enrollment.
16. Unable to swallow capsules, malabsorption syndrome, disease significantly affecting gastrointestinal function, resection of the stomach or small bowel, symptomatic inflammatory bowel disease or ulcerative colitis, or partial or complete bowel obstruction.
17. Concurrent use of warfarin or other Vitamin K antagonists (eg, phenprocoumon).
18. Requires treatment with a strong cytochrome P450 (CYP) 3A inhibitor (see [Appendix 4](#)).
19. Any life-threatening illness, medical condition including uncontrolled Diabetes Mellitus, or organ system dysfunction that, in the opinion of the Investigator, could compromise the subject's safety or put the study outcomes at undue risk.
20. Currently active, clinically significant hepatic impairment Child-Pugh class B or C according to the Child-Pugh classification
21. Known hypersensitivity to lenalidomide (or thalidomide) or rituximab.
22. Lactating or pregnant.
23. Unwilling or unable to participate in all required study evaluations and procedures.
24. Unable to understand the purpose and risks of the study and to provide a signed and dated informed consent form (ICF) and authorization to use protected health information (in accordance with national and local subject privacy regulations).

5. TREATMENT OF SUBJECTS

5.1. Phase 1b Dose Escalation and Stopping Rules

This is an open-label dose escalation study using a 3+3+3 design. Before applying the dose escalation rules, 3 subjects in any given cohort must have completed the DLT observation period which is defined as 28 days (1 cycle of therapy followed by laboratory evaluation for toxicity on Cycle 2 Day 1, Study Day 29). The modified 3+3+3 design defines the MTD to have been exceeded when ≥ 3 out of 9 subjects in a cohort experience a DLT. If there are 3 DLTs in Dose Level 1, Dose Level -1 will be enrolled.

After completion of Cohort 1 at Dose Level 1, due to 3 DLTs in 7 evaluable subjects, a cohort at Dose Level -1 was opened. After completion of the Dose Level -1 cohort, if $< 33\%$ of subjects experience a DLT, dose re-escalation to higher dose levels starting with the lenalidomide dose of 15 mg may occur. Due to the fact that the subject population studied is significantly ill and an inability to complete the DLT observation period may occur due to progression of disease, additional subjects may be screened and enrolled in each cohort. The DLT rules will continue to apply whereas if 1 DLT is observed, the cohort will be expanded to 6, and if 2 DLTs occur, the cohort will be expanded to 9.

Enrollment in a cohort will proceed as follows:

- If no dose limiting toxicity (DLT) is observed during the DLT observation period in the initial 3 subjects of a cohort, dose escalation to the next higher dose level cohort will occur.
- If 1 DLT is observed, 3 additional subjects will be enrolled at the same dose level for a total of at least 6 subjects. If no further DLT(s) are observed, escalation to the next higher dose level cohort will occur.
- If a second DLT is observed, 3 additional subjects may be enrolled at the same dose level for a total of at least 9 subjects. If no further DLTs are observed, dose escalation to the next higher dose level will occur. Note: If appropriate, no further expansion of this cohort will occur if significant safety concerns are recognized after the first 6 subjects are enrolled.
- If ≥ 3 DLTs are observed in the 9 subjects, then enrollment will stop at the third DLT observation and enrollment into a cohort at a lower dose level (with the exception of Cohort -1) will be considered.
- After enrollment of a cohort at Dose Level -1 (10mg lenalidomide) and if $<33\%$ of subjects experience a DLT, dose re-escalation to higher dose levels starting with the lenalidomide dose of 15 mg may occur.

If a subject experiences a DLT during the DLT observation window, the subject may continue study treatment, if continued clinical benefit from study treatment is expected per the treating physician and the toxicity observed is manageable; the Sponsor should be notified in this case.

The decision to proceed to the next dose level will be made in a Dose Level Review Committee Meeting by the Sponsor in conjunction with the Investigators after careful consideration of all available safety and laboratory information. Safety data from subjects on preceding cohorts that remain on continuous dosing will also be considered.

Dose escalation will occur at the planned dose levels until the MTD is determined or until the highest dose level is tested. The MTD is defined as the highest dose at which $<33\%$ of the subjects enrolled in a cohort experience a DLT. If all evaluated dose levels demonstrate an observed incidence of DLT in $<33\%$ of subjects, the MTD of lenalidomide in the combination has not been reached. At least 6 subjects will be treated at the MTD or in any cohort that supports the Phase 2. The assessment of DLT will follow the guidelines provided in the Common Terminology Criteria for Adverse Events ([CTCAE, version 4.03](#)).

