1.17. PCYC-1123-CA Phase 1b Data Summary

As of 25 April 2016, a total of 38 subjects were enrolled (37 treated) in Cohort 1 (13 subjects enrolled, 12 treated), Cohort -1 (7 subjects enrolled), Cohort 1+ (9 subjects enrolled) and Cohort 2 (9 subjects enrolled).

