1.1.1 Phase 1b

In the dose escalation portion of the study, up to four cohorts may be explored, and the lenalidomide dose escalation will follow the 3+3+3 principle for the maximum tolerated dose (MTD) determination. Due to the fact that the subject population studied is significantly ill, and an inability to complete the dose-limiting toxicity (DLT) observation period may occur due to progression of disease, additional subjects may be screened and enrolled in each cohort. The DLT rules will continue to apply whereas if 1 DLT is observed, the cohort will be expanded to 6, and if 2 DLTs occur, the cohort will be expanded to 9.

Ibrutinib will be administered orally once daily at 560 mg and will be initiated on Day 1 of the first cycle. Treatment will be continuous (without interruption) and will continue until disease progression or unacceptable toxicity. Lenalidomide will be administered orally once daily at the dose designated by cohort on Days 1-21 of each 28-day cycle and will continue until disease progression or unacceptable toxicity. Rituximab 375 mg/m² will be administered intravenously (IV) on Day 1 of each 28-day (4-week) cycle for 6 cycles.

If 3 subjects in Cohort 1 experience a DLT, dose level -1 was planned to be enrolled (Table 1). After completion of Cohort 1, due to 3 DLTs in 7 evaluable subjects, a cohort at Dose Level -1 was opened. After completion of the Dose Level -1 cohort, if <33% of subjects experience a DLT, dose re-escalation to higher dose levels starting with the

lenalidomide dose of 15 mg may occur. If the dose level of 20 mg lenalidomide is determined to be safe and tolerated in the Phase 1b, this dose will be considered the recommended Phase 2 dose (RP2D), and a Phase 2 cohort with 20 mg lenalidomide will be initiated. Concurrent with the Phase 2 at 20 mg lenalidomide, a Phase 1b cohort with 25 mg lenalidomide may be initiated. If the interim analysis of the 20 mg lenalidomide cohort is negative, the 25 mg lenalidomide dose may be used in an additional cohort in the Phase 2, if safe and tolerated in the Phase 1b.

Table 1: Phase 1b Dose Levels

28-Day Dosing Cycle	Ibrutinib ^a	Lenalidomide ^b	Rituximab ^c
Dose Level -1^d	560 mg once daily	10 mg	375 mg/m ²
Dose Level 1 = starting dose (Cohort 1 & 1+)	560 mg once daily	15 mg	375 mg/m ²
Dose Level 2 (Cohort 2)	560 mg once daily	20 mg	375 mg/m ²
Dose Level 3 (Cohort 3)	560 mg once daily	25 mg	375 mg/m ²

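### Protocol 5.1 defines the MTD by the DLT rate among subjects enrolled, so subjects who never completed the DLT window dilute the rate and the definition can conflict with the section's own three-DLT rule

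*Protocol*

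**What the plan says.** Protocol 5.1 contains two statements about the MTD.

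- The definition: the MTD is the highest dose at which fewer than 33% "of the subjects enrolled in a cohort experience a DLT".
- The count rule: the MTD has been exceeded when three or more "out of 9 subjects in a cohort experience a DLT". Enrolment stops at the third DLT.

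The surrounding text in 5.1 points to observed subjects as the basis:

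- Before the escalation rules apply, "3 subjects in any given cohort must have completed the DLT observation period".
- Because ill subjects may not finish the window, "additional subjects may be screened and enrolled in each cohort".
- After a second DLT, the cohort may be expanded "for a total of at least 9 subjects", which is a minimum and not a cap.
- Cohort 1 is read on evaluable subjects: "due to 3 DLTs in 7 evaluable subjects, a cohort at Dose Level -1 was opened". SAP 1.1.1 repeats this: "After completion of Cohort 1, due to 3 DLTs in 7 evaluable subjects".

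For enrolment at 25 April 2016, Protocol 1.17 reports "a total of 38 subjects were enrolled (37 treated) in Cohort 1 (13 subjects enrolled, 12 treated". It then gives 7 enrolled in Cohort -1, 9 in Cohort 1+ and 9 in Cohort 2.

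Protocol 5.2 says that most non-completers are replaced, but not that they leave the count of enrolled subjects. Neither Protocol 10.2 nor SAP 2.1 defines a DLT-evaluable population, and SAP Table 5 only lists DLTs. SAP 1.2.1 makes the MTD or RP2D a Phase 1b primary endpoint.

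**The concern.** A DLT rate means something only among subjects who were observed long enough to show a DLT, or who had one. Subjects who leave early because of progression contribute no DLT and no complete observation. In an enrolled denominator they count as if they had tolerated the dose, and so does a subject who was enrolled but never treated. The protocol expects such subjects and permits extra enrolment to make up for them, so the dilution is built into the definition.

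The consequence is that one set of data can be read in two ways. The count rule may say that the MTD is exceeded at a dose where the rate sentence says the DLT rate is acceptable. For a primary endpoint, the answer should not depend on which sentence of the section is applied.

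**Working it through.** **Inputs.** The 33% threshold, its enrolled denominator and the count rule of 3 out of 9 are from Protocol 5.1. Cohort 1's 3 DLTs and 7 evaluable subjects are from Protocol 5.1 and SAP 1.1.1. Its 13 enrolled and 12 treated are from Protocol 1.17.

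**Step 1: do the two rules agree on evaluable subjects at the planned cohort sizes?** A rate below 33% allows 0 of 3, at most 1 of 6 (1/6 = 16.7%; 2/6 = 33.3% fails) and at most 2 of 9 (2/9 = 22.2%; 3/9 = 33.3% fails). So 3 of 9 fails both the rate condition and the count rule. The protocol's two statements are consistent at these sizes.

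**Step 2: where do they part on enrolled subjects?** With 3 DLTs, the rate is 3/n for n enrolled:

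| n | 3/n | Below 33%? | Count rule |
|---|---|---|---|
| 7 | 42.9% | no | exceeded |
| 8 | 37.5% | no | exceeded |
| 9 | 33.3% | no | exceeded |
| 10 | 30.0% | yes | exceeded |
| 11 | 27.3% | yes | exceeded |
| 12 | 25.0% | yes | exceeded |
| 13 | 23.1% | yes | exceeded |

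The conflict starts at 10 enrolled. The number of non-evaluable subjects needed to reach 10 is 10 − 7 = 3 with 7 evaluable, 10 − 8 = 2 with 8, and 10 − 9 = 1 with 9.

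**Step 3: Cohort 1.**

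- Enrolled: 3/13 = 23.1%, below 33%.
- Treated: 3/12 = 25.0%, below 33%.
- Evaluable: 3/7 = 42.9%, not below 33%.

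The enrolled and evaluable numbers come from different sections. The 13 is a count at the April 2016 cut, and the 7 is the basis for opening Dose Level -1. The text does not say that they share a date. The threshold of 10 in Step 2 does not depend on them.

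**Step 4: is changing the denominator enough?** Not quite. With 10 evaluable subjects and 3 DLTs, 3/10 = 30.0% still passes the rate condition while the count rule says exceeded. Since 9 is only a minimum, the plan also has to say which rule prevails.

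**Step 5: which cohorts are exposed?** Cohorts -1, 1+ and 2 had 7, 9 and 9 enrolled at the cut, all below 10. Cohort 3 had not yet enrolled. Phase 1b was planned at about 46 subjects, and 46 − 38 = 8 remained.

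**The case against.** The best reply is that the intent is plain. The escalation rules wait for completed windows, Cohort 1 is read on evaluable subjects, and replacing non-completers suggests that they were meant to drop out of the calculation. The count rule sits in the same section and stops enrolment at the third DLT. A Dose Level Review Committee decides escalation on all safety data. The objective is the MTD and/or the recommended Phase 2 dose, and no planned SAP analysis computes a DLT rate. The plan also leaves only about 8 Phase 1b places for Cohort 3.

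Most of this stands, and it is why the point is minor. It does not repair the definition. Replacing a subject adds one without removing the other from those enrolled, and Protocol 1.17 separates enrolled from treated, so the word is used literally elsewhere. The figure of 46 is approximate, and extra enrolment is allowed in each cohort, so 10 or more in Cohort 3 is possible though not planned.

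Three stronger readings are tempting and are not supported:

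- A reader might infer that 15 mg satisfied the MTD definition in Cohort 1. It met only the rate condition, and only on enrolled or treated subjects. The definition asks for the highest such dose, and the trial went on to 20 mg and planned 25 mg. The DLT criteria were also revised after Cohort 1.
- A reader might scale the 33% cut-off by Cohort 1's ratio of enrolled to evaluable subjects and conclude that a much higher DLT rate was tolerated. The count rule acts at the third DLT, well before any such cut-off could operate.
- A reader might infer from the missed-dose replacement wording in Protocol 5.2 that a replaced subject's DLT is discarded. The text never says so, and the same section lists a toxicity delay of more than 7 days as a DLT.

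**Conclusion.** The concern holds as a minor defect in the definition of a Phase 1b primary endpoint. Read literally, the enrolled denominator dilutes the DLT rate, and with 3 DLTs it contradicts the count rule at 10 or more enrolled. Cohort 1 illustrates the gap: 23% of enrolled against 43% of evaluable subjects, with the caveat that the two counts may differ in date.

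No conduct error is shown. The count rule was applied to Cohort 1, Dose Level -1 was opened, 15 mg was tested again as Cohort 1+, and the committee governed escalation. What remains exposed is how the MTD is declared or reported, chiefly for Cohort 3, whose final size and DLT count are not in the documents.

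This rests on a literal reading of the MTD sentence and on the enrolment figures in Protocol 1.17. Parts of Protocol 1.13 and 1.17 were not available to read, so a reconciliation of the Cohort 1 counts there cannot be excluded.

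**What to change.** - In the MTD sentence of Protocol 5.1, replace the enrolled denominator with DLT-evaluable subjects: those who had a DLT in the window, or who completed the 28-day window with the required dosing.
- Use that set in every rule stated as a rate below 33% or as a count out of 9, including re-escalation from Dose Level -1 and the statement that the MTD has not been reached.
- State that three or more DLTs mean the MTD is exceeded even when more than 9 subjects are evaluable.
- Use the same denominator in the clinical study report, which SAP Section 6 places at the final follow-up analysis.

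No new data or visits are needed. The costs are a protocol amendment, which under Protocol 12.15 needs ethics approval before it takes effect at each site; reported DLT rates somewhat higher than on the enrolled denominator; and a stricter rule at 10 or more evaluable subjects, where 3/10 = 30.0% would otherwise pass.
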